## Protocol: Glial Regulators for Testing Comorbid Posttraumatic Stress Disorder and Substance Use Disorders

### Hypotheses

Hypothesis 1: Participants receiving N-acetylcysteine (NAC), as compared to placebo, will demonstrate significantly greater reduction in SUD severity and craving from baseline to end of treatment (week 8).

Hypothesis 2: Participants receiving N-acetylcysteine (NAC), as compared to placebo, will demonstrate significantly greater reduction in PTSD severity from baseline to end of treatment (week 8).

Hypothesis 3: Prefrontal cortex-amygdala connectivity at rest and in response to cues will predict reduction in SUD and PTSD severity.

### METHODS

**Overview:** A randomized, double-blind, placebo-controlled clinical trial among individuals (N=90) with SUD and PTSD will be conducted to test the hypothesis that N-acetylcysteine (NAC) will significantly reduce SUD severity, craving, and PTSD symptoms. A subset of enrolled subjects between the ages of 21-40 will complete neuroimaging procedures before and after treatment. All procedures will be reviewed by the MUSC IRB and the Ralph H. Johnson VA Research and Development committee prior to study start.

**Participants:** Ninety male and female participants between the ages of 18 to 75 with current AUD/SUD and comorbid PTSD or sub-threshold PTSD will be recruited to participate in the study.

**Recruitment:** Primary recruitment sites include (1) the Ralph H. Johnson VAMC outpatient Substance Treatment and Recovery Clinic (STAR) and (2) the PTSD Clinical Team (PCT).

**Inclusion/Exclusion Criteria:** To be included, subjects must (1) be 18-75 years old, (2) meet DSM-5 criteria for current PTSD or subthreshold PTSD, and (3) meet DSM-5 criteria for current AUD/SUD. Exclusion criteria include: (1) schizophrenia, bipolar disorder or an eating disorder; (2) any significant medical illness (e.g., asthma) that may adversely affect safety or study participation; (3) psychotropic medication initiation within 4 weeks of study participation or use of the following medications: carbamazepine, phenytoin, nitrous oxide, methotrexate, 6-azauridine triacetate, nitroglycerin or any other medication that may have an adverse interaction with NAC; (4) pregnant or nursing women; and (5) clinically significant suicidal ideation and intent.

**General Procedures:** Interested individuals will be screened for eligibility. Individuals who meet inclusion/exclusion criteria will be invited to come into the office for a comprehensive baseline assessment. Potential participants will be given a full description of the study and asked to read and sign an IRB-approved informed consent form before any study procedures or assessments are conducted. Baseline assessment will include diagnostic interviews, history and physical examination, assessment of concomitant medications, self-report questionnaires, breathalyzer and urine drug screen (UDS), and pregnancy test for females. Ineligible participants will be referred clinically for treatment. Immediately following the baseline visit, eligible participants between the ages of 21-40 will complete a neuroimaging session (described in the Neuroimaging Component section) prior to medication initiation. This same subset of participants will complete a second neuroimaging scan during week 8 prior to medication discontinuation. All participants will enter an 8-week, randomized, double-blind, placebo-controlled trial in which they will be seen once weekly.

**Study Medication, Dosage, and Administration:** The starting and continuation dose of NAC will be 1200mg bid (2400mg/day). Medication will be dispensed weekly and participants will be asked to return the prior week's medication container in order to account for unused medication and to assess medication compliance. Equivalent number of matching placebo capsules will be dispensed. Study medications (USP-grade NAC and matched placebo capsules) will be packaged by Pitt Street Pharmacy in Mount Pleasant, SC and dispensed to participants by the medical clinician. All NAC and placebo capsules will also contain riboflavin 25 mg, which will be used as a biomarker for medication compliance. Participants who wish to take a multivitamin during the treatment phase of the study will be given a multivitamin that does not contain riboflavin. Treatment assignment will follow a pre-

## Protocol: Glial Regulators for Testing Comorbid Posttraumatic Stress Disorder and Substance Use Disorders

arranged randomization scheme and be carried out by a pharmacist not involved in clinical management of participants (to preserve the double-blind design). Subjects will be maintained at the target dose for 8 weeks. Side effects and adverse events will be evaluated weekly.

**Cognitive Behavioral Intervention:** Participants will receive 1-hour each week of manual-based, cognitive behavioral therapy (CBT) for AUD/SUD. Receipt of weekly CBT during the treatment phase will facilitate retention and medication adherence, ensure that all participants receive adequate psychosocial support regardless of medication arm, and enhance statistical power (Carroll et al., 2004). Sessions from the Cognitive Behavioral Coping Skills Manual (Kadden et al., 2003) will be used, for example: Coping with Cravings and Urges to Use, Managing Thoughts about Alcohol/Drug Use, Problem Solving, Alcohol/Drug Refusal Skills, Planning for Emergencies and Coping with a Lapse, and Managing Negative Moods and Depression. All Study Therapists will complete a formal training of the intervention. To help maintain treatment integrity, we will use a manualized treatment, provide intensive bi-weekly supervision to reinforce and sustain clinicians' skills in therapy delivery, and monitor fidelity to the treatment manual using methods developed in the NIMH Collaborative Study to prevent therapist "drift" (DeRubeis et al., 1982).

**Assessment Instruments:** After the informed consent procedure, subjects will complete a battery of assessments. The instruments to be used were selected because many are standardized, have good psychometric properties, are widely used and have been used by our research group. The primary clinical outcomes include: alcohol/substance use severity (TLFB), craving (OCDS), and PTSD symptom severity (CAPS-5).

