We plan to use REDCap for data capture and management. REDCap (Research Electronic Data Capture) is a software toolset and workflow methodology for electronic collection and management of research and clinical trial data (Harris et al., 2008; Harris et al., 2007). REDCap provides secure, web-based flexible applications, including real time validation rules with automated data type and range checks at the time of entry. Exports are made available for several statistical packages including SPSS, SAS, SATA, R and Microsoft Excel.

**Power and Sample Size Estimation.** It is expected that subjects treated with NAC, as compared to placebo, will exhibit significantly lower PTSD symptoms and craving at week 8. The effect sizes for these analyses ( $d = 1.27$ ,  $d = 1.03$ , respectively) are based on our PoP data. A sample size of 26 would provide power ( $1-\beta$ ) of .80 to detect a large effect size with a Type 1 error protection level of .05 (Cohen, 1988). It is expected that NAC, as compared to placebo, will exhibit significantly lower AUD/SUD severity at week 8. To date, no published studies have examined NAC for the treatment of AUD. Assuming a medium effect size ( $d = .2$ ), with a Type 1 error protection level of .05 and  $(1-\beta) = .80$ , a total sample of 58 would be required. Recent unpublished pilot data conducted by our group examining the effects of NAC vs. placebo on standard number of drinks among patients with cocaine dependence and comorbid AUD ( $n=28$ ) found a statistically significant treatment group effect. With regard to neuroimaging, a recent study of 29 individuals (PTSD=14, controls=15) observed significant differences in PFC-AMY resting state connectivity (Sripada et al., 2012). The effect size for this difference was 0.8 (Cohen's  $d$ ). Thus, power ( $1-\beta$ ) reaches .80 with a total sample size of  $N=26$  (two-tailed,  $\alpha = .05$ ). Another study of 45 cocaine-dependent individuals showed that lower PFC-AMY connectivity at baseline predicted relapse (McHugh et al., 2014). The effect size for this reduction was 1.0. Thus, power ( $1-\beta$ ) reaches .80 with  $N=34$  subjects (two-tailed,  $\alpha = .05$ ).

**Hypotheses:** The hypotheses and statistical approaches for testing each hypothesis are listed below.

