## Protocol: Glial Regulators for Testing Comorbid Posttraumatic Stress Disorder and Substance Use Disorders

total number of standard drinks consumed and the OCDS total score as the primary outcomes. A Poisson distribution will be assumed with a logarithm link function to assess the effects of NAC treatment. Data collected in substance abuse studies often contain a preponderance of zeros, and these zeros in the distribution can be considered sampling zeros in the Poisson process (Bandyopadhyay et al., 2011). If this excess is present in the distribution, two-part Hurdle models (Poisson and NB) will be explored (Cragg et al., 1971). The hurdle part of the model will allow us to estimate the probability of abstinence during the study period (as an odds ratio) while the Poisson/NB portion will allow for the assessment of the risk of an increase in using days beyond zero during the study period (as a risk ratio). Baseline alcohol/substance use and craving will be included in pertinent models as covariates. Additional alcohol/substance use outcomes will be assessed: change in percent drinking days, percent heavy drinking days, EtG, and VAS craving levels.

Hypothesis 2: NAC treatment will result in significantly greater reduction in PTSD severity (CAPS-5) as compared to placebo. To test this hypothesis, generalized linear mixed effects regression models with a Gaussian distribution will be developed to assess group differences while adjusting for baseline CAPS-5 scores. Assumptions of residual normality and homoscedasticity will be checked using statistical test and graphical methods (Residual and Q-Q plots, and Shapiro-Wilk tests) and transformation will be done as necessary. Restricted maximum likelihood methods will be used to estimate the fixed effects and variance components. Additional outcomes (e.g., PCL-5, CAPS-5 symptom subscales) will be examined.

Hypothesis 3A: Prefrontal cortex-amygdala connectivity at rest and in response to alcohol/drug vs. neutral cues will predict reduction in alcohol/substance use severity (total standard drinks).

Hypothesis 3B: Prefrontal cortex-amygdala connectivity at rest and in response to trauma vs. neutral cues will predict reduction in PTSD severity (CAPS-5).

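### Three unranked primary outcomes are planned with .05 used in full for each power statement, and no multiplicity or success rule says what counts as a positive result

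*Combined protocol and SAP*

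**What the plan says.** METHODS, Assessment Instruments, names the outcomes: "The primary clinical outcomes include: alcohol/substance use severity (TLFB), craving (OCDS), and PTSD symptom severity (CAPS-5"). No order of importance is given.

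The analysis text for Hypothesis 1 takes the "total number of standard drinks consumed and the OCDS total score as the primary outcomes". CAPS-5 has its own model: "Hypothesis 2: NAC treatment will result in significantly greater reduction in PTSD severity (CAPS-5) as compared to placebo".

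Power and Sample Size Estimation treats the outcomes in two groups. For PTSD and craving it says: "It is expected that subjects treated with NAC, as compared to placebo, will exhibit significantly lower PTSD symptoms and craving at week 8". It gives pilot effect sizes of 1.27 and 1.03 and a sample size of 26 "with a Type 1 error protection level of .05". For AUD/SUD severity it uses the full level again: "Assuming a medium effect size ( $d = .2$ ), with a Type 1 error protection level of .05".

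The text on the clinical analyses gives no significance level, so .05 for those tests comes only from the power section. Two-tailed testing is stated only for the imaging calculations. The only correction for multiple testing in the document is the cluster threshold for the imaging maps.

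**The concern.** With three primaries and no rule, the plan does not say whether the trial succeeds on one outcome, on all of them, or hypothesis by hypothesis. Hypothesis 1 has the same gap on a smaller scale: it has two primary outcomes, and nothing says whether a difference on drinks alone, or on craving alone, would support it.

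A rule left open until the data are seen can be settled in favour of whichever outcome came out significant. If NAC had no effect on any of the three, a claim of success on any one of them would then be wrong more often than the .05 in the power section leads a reader to expect. What is at stake is how a positive claim is read. The unadjusted effect estimates are not affected.

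**Working it through.** **Inputs from the document.** Three primary outcomes, two of them in Hypothesis 1; .05 and power .80 in each clinical power statement; effect sizes 1.27 (PTSD), 1.03 (craving) and .2 (AUD/SUD severity); N = 90.

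**Assumptions.** Two-sided clinical tests, 1:1 allocation (45 per arm), full retention. The document gives no correlation between outcomes, so a range is shown.

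**Step 1: the plan's own figure.** Taking a large effect as d = 0.8, n per arm = 2(z₀.₉₇₅ + z₀.₈₀)²/d² = 2(1.960 + 0.842)²/0.64 = 24.5, so 25; a two-sample t-test gives 26. The stated 26 therefore reproduces as a per-arm number at two-sided .05. It also reproduces as a total for a one-sided t-test at d = 1.03, so it does not settle the sidedness. On either reading the whole .05 goes to one outcome. (The other figure, a total of 58 for d = .2, does not reproduce: a two-sided t-test needs 788. That is a separate matter.)

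**Step 2: at least one false positive.** For k independent tests at .05 the chance is 1 − (1 − .05)^k.

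- k = 3: 1 − .95³ = .1426
- k = 2: 1 − .95² = .0975

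For equally correlated normal test statistics, by numerical integration:

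| Correlation | Three primaries | Hypothesis 1 (two) |
|---|---|---|
| 0 | 14.3% | 9.8% |
| .3 | 13.6% | 9.5% |
| .5 | 12.5% | 9.1% |
| .7 | 10.9% | 8.3% |
| .9 | 8.4% | 7.0% |

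For three outcomes the ratio to .05 runs from 14.3/5 = 2.9 down to 8.4/5 = 1.7.

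**Step 3: the opposite success rule.** If Hypothesis 1 required both outcomes to be significant, the false-positive chance with no effect on either is .05 + .05 − P(at least one). That is .10 − .0975 = .0025 if independent and .10 − .0907 = .009 at correlation .5. Nothing is inflated.

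**Step 4: what Holm would cost.** Holm compares the smallest p-value with .05/3 = .0167, the next with .025 and the largest with .05, stopping at the first failure. Simulated power (45 per arm, outcome correlation .3, normal approximation), unadjusted → Holm:

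| Effects (CAPS-5, OCDS, drinks) | CAPS-5 | OCDS | Drinks |
|---|---|---|---|
| 1.27, 1.03, .2 | >.999 → >.999 | .998 → .996 | .16 → .16 |
| 1.27, 1.03, .5 | >.999 → >.999 | .998 → .996 | .66 → .66 |
| .64, .52, .2 | .86 → .76 | .69 → .58 | .16 → .14 |
| .64, .52, .5 | .86 → .79 | .69 → .62 | .66 → .59 |

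The last two rows halve the pilot effects. The drinking effect of .5 is an assumption, shown because the plan calls its .2 medium. Drinking keeps its power in the first two rows because the other two outcomes are nearly always rejected first.

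**The case against.** The strongest reply is that nothing stated in the plan is breached. The .05 is attached to each power calculation and is never described as applying to the trial or to a hypothesis. That stands. A reader might infer that the stated Type 1 error protection fails; the document does not support this, because each test taken alone can still run at .05.

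Second, Hypothesis 1 is worded with an *and* joining severity and craving, and the Overview joins all three outcomes in the same way. If that means every outcome must be significant, there is no inflation (Step 3). A reader might also infer that Hypothesis 1 has been shown to carry a 9% to 10% error rate. That is not shown either, since the figure depends on allowing either outcome to suffice. But the *and* describes what is expected and is not a decision rule, so the plan does not establish the all-must-win reading.

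Third, substance use and PTSD sit under separately numbered hypotheses, and adjusting across them is a choice that nothing in the document requires. This is fair. It does not help within Hypothesis 1, which has two primaries of its own.

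Fourth, the cost of adjustment is small only if the pilot effects are real. This also stands: all three outcomes can lose power when effects are moderate. The power figures also use standardised mean differences, whereas the planned drinking model is Poisson or hurdle.

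**Conclusion.** The point holds as a gap in specification: three unranked primaries, .05 used in full for each power statement, and no multiplicity or success rule. If any one significant primary may be claimed, the chance of at least one false positive is 14.3% under independence and 8.4% at correlation .9; within Hypothesis 1 it is 9.8% and 7.0%. All of these exceed .05. They rest on two-sided testing at .05 for each outcome, which is inferred, and on assumed correlations. They describe what the plan permits, not an error in its arithmetic. Possible further inflation, from the two parts of a hurdle model or from covariates chosen by significance, is not counted.

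**What to change.** Before unblinding, add to the Statistical Analyses section that:

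- total standard drinks, OCDS total and CAPS-5 total form one primary family, tested with the Holm procedure at two-sided family-wise .05;
- drinking contributes a single pre-named p-value. If the hurdle model is used it yields both an odds ratio and a risk ratio, so the plan must say what enters Holm, for example a joint test of both parts;
- unadjusted estimates and confidence intervals are reported alongside;
- all other outcomes are supportive.

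Holm keeps family-wise error at or below .05 whatever the correlation. The cost is a short addition to the plan, with no new data or participants. The price in power is negligible at the pilot effects. If those effects are halved, it is roughly .07 to .11 for CAPS-5 and OCDS, and .02 to .07 for drinking, as tabulated above.

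A stated rule that both Hypothesis 1 outcomes must be significant would also close the gap within that hypothesis. Its power could not exceed that of drinking alone: .66 at d = .5 or .16 at d = .2.

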### **General Diagnostic and Inclusion/Exclusion Criteria**

- Demographics and Military Service Characteristics Form: This form measures demographics (e.g., age, race, gender, education, marital status) and military service information, such as branch and rank.
- Treatment Services Review: This form obtains information about the participant's ongoing/new treatment for alcohol/substance use and PTSD.
- Mini International Neuropsychiatric Interview 7.0 (MINI 7.0; Sheehan et al., 1998): The MINI will be used to diagnose AUD, SUD, and confirm other exclusionary psychiatric diagnoses.
- History of Head Injuries: A questionnaire that will be administered at Baseline, and Week 8 for anyone participating in fMRI, to assess for head injuries.

### **Vital Signs, Adverse Events and Medication Compliance**

- Vital Signs: Orthostatic blood pressure, pulse measurements, weight and body mass index (BMI) calculations will be measured at baseline, Week 4, and Week 8.
- Adverse Events (AEs): AEs will be assessed at baseline, weekly during treatment, and at follow-up. The type of AE, severity of the AE, duration of the AE, and relationship of AE to study medication will be recorded.
- Concomitant Medications: All concomitant medications will be recorded on a standard form throughout the study. Multivitamins supplied by the study will be recorded and inquiries will be made about daily compliance.
- Medication Accountability Log: This is a document describing a one-week schedule recording days of study medicine taken. Returned medication packages will have capsules counted and recorded.
- Riboflavin Test: All medication capsules, NAC and placebo, will contain 25mg of riboflavin. A urine assay will be collected at medication initiation (at baseline for telehealth participants), week 4 and week 8 to test for medication compliance.

Protocol: Glial Regulators for Testing Comorbid Posttraumatic Stress Disorder and Substance Use Disorders

**Table 1. Assessment Instruments and Timeline**

Instrument	Baseline	Medication Initiation	Medication and Symptom Monitoring								Follow Up
	Weeks → -1	0	1	2	3	4	5	6	7	8	1 & 3 Mth
Demographic Data	X										
History and Physical Examination	X										
MINI Diagnostic Interviews	X										
Concurrent Medications Form	X	X	X	X	X	X	X	X	X	X	X
Vital Signs	X					X				X	
Medication Log		X	X	X	X	X	X	X	X	X	
Urine Pregnancy Test for Females	X					X				X	
Urine Drug Screen: UDS	X					X				X	X
Riboflavin Test		X				X				X	
Adverse Events		X	X	X	X	X	X	X	X	X	X
Breathalyzer/Saliva BAC Tests	X	X	X	X	X	X	X	X	X	X	X
Timeline Follow- Back: TLFB	X	X	X	X	X	X	X	X	X	X	X
CIWA-AR	X										
Visual Analog Scales; VAS	X	X	X	X	X	X	X	X	X	X	X
Obsessive Compulsive Drinking Scale: OCDS	X	X	X	X	X	X	X	X	X	X	X
Ethyl glucuronide (EtG)		X				X				X	X
Clinician Administered PTSD Scale: CAPS-5	X					X				X	X
PTSD Checklist: PCL-5	X		X	X	X	X	X	X	X	X	X
Life Events Checklist: LEC-5	X										
Childhood Trauma Questionnaire: CTQ-SF	X										
Beck Depression Inventory-II: BDI-II	X		X	X	X	X	X	X	X	X	X
Deployment Risk & Resiliency Inventory-2	X										
Columbia Suicide Severity Rating Scale	X					X				X	X
Penetration of the Blind Questionnaire										X	
AUDIT	X										
Cognitive Testing		X				X				X	
Blame Questionnaire	X									X	
Fagerstrom	X										
Coping Inventory	X									X	
Visual Analog Scale: VAS - fMRI	X									X	
History of Head Injuries BL	X										
History of Head Injuries FU										X	
Satisfaction Questionnaire										X	X
Treatment Services Review	X	X	X	X	X	X	X	X	X	X	X
Neuroimaging Procedures	■										■
Cognitive Behavioral Therapy: CBT			◆	◆	◆	◆	◆	◆	◆	◆	

**Alcohol/Substance Use Disorder and Craving**

- **Timeline Follow-Back (TLFB; Sobell & Sobell, 1992):** The TLFB obtains retrospective self-report of substance use by using a calendar and memory prompts to stimulate recall. Quantity and frequency assessments are made using this instrument (e.g., total number of standard drink units, percent of days using) as well as abstinence (yes/no). TLFB yields consistently high test-retest correlations and correlates well with other self-reports and collateral reports. The TLFB will assess consumption of alcohol (standard drink units) for 60 days prior to study entry, during the treatment and follow-up phase. Use of nicotine and other drugs of abuse, including prescription drugs, will also be assessed using the TLFB.

## Protocol: Glial Regulators for Testing Comorbid Posttraumatic Stress Disorder and Substance Use Disorders

- Alcohol Breathalyzer Test will be used to measure blood alcohol concentration (BAC) on a weekly basis for in person visits. Samples reading >0.01 g/dl will be considered positive.
- Alcohol Saliva Test will be used to measure blood alcohol concentration (BAC) on a weekly basis for telehealth visits. In front of the camera, participants will open the one time use test strip, place strip on tongue for 10 seconds, then hold test strip and a color chart to the camera for a study team member to assess. Samples reading >0.01 g/dl will be considered positive.
- Obsessive Compulsive Drinking Scale (OCDS) (Anton et al., 1995): The OCDS is a 14-item self-report measure of craving with high internal consistency and concurrent validity, and good predictive validity of future drinking (Anton et al., 1995; Drobles & Thomas, 1999). It will be used to assess craving.
- Visual Analog Craving Scale (VAS): A Modification of the Within Session Rating Scale (Childress et al., 1986) will be used to assess subjective ratings including craving (amount, frequency), stress and mood, with anchors from 0 = “none” to 10 = “extreme”.
- Visual Analog Scale (VAS) fMRI: A modification of the Within Session Rating Scale (Childress et al., 1986) will be used to assess subjective ratings including craving and stress before and after the fMRI scan.
- Clinical Institute Withdrawal Assessment of Alcohol-Revised (CIWA-Ar) (Sullivan et al., 1989): The CIWA-Ar is a widely used, 10-item clinician administered instrument that will be used to assess alcohol withdrawal symptoms. Subjects experiencing significant withdrawal, as evidenced by a score of  $\geq 10$ , will be assessed by the Study Physician ([name]) and referred clinically for medically supervised detoxification.
- Alcohol Use Disorders Identification Test (AUDIT) (Babor et al., 2001): The AUDIT is a 10-item self-report screening measure, developed by the World Health Organization (WHO), with three subscales (alcohol consumption, drinking behavior, and alcohol-related problems). Items are summed for a total score of 40. The AUDIT has good internal consistency ( $\alpha = .80-.93$ ) as well as sensitivity and specificity.
- Urine Drug Screen (UDS) tests: Urine samples will be tested with a Multi-Drug Panel Test, which allows for the detection of THC/Marijuana, Cocaine, Phencyclidine, Opioids, Methamphetamines, Amphetamines, Barbiturates, and Benzodiazepines.
- Ethyl glucuronide (EtG): The conjugated alcohol metabolite EtG remains positive in urine for several days following cessation and is a useful biomarker of drinking in outpatient settings (Litten et al., 2010). This will be used as a biologic assessment of drinking, as breathalyzer tests only assess very recent alcohol use. The assay will be done at MUSC on samples collected at medication initiation, week 4, week 8 (end of treatment), and the follow ups.
- Fagerstrom Test for Nicotine Dependence (FTND): Assesses the intensity of physical addiction to nicotine related to cigarette smoking. There are six questions that provide a total score range of 0-10, higher scores indicate a higher physical dependence (Heatherton, et al., 1991). It will be administered at baseline.

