### **Associated Areas of Functioning**

- Deployment Risk and Resiliency Inventory-2 (DRRI-2): The DRRI-2 (Vogt et al., 2012) is a suite of 17 individual scales that assess key deployment-related risk and resilience factors with demonstrated implications for Veterans' long-term health. The following subscales will be used to assess deployment factors: Combat Experiences. We will use the Post-Deployment Life Events and Support scales to evaluate post-deployment factors for Veterans.
- CNS Vital Signs Cognitive Testing: A battery of two tests (Stroop & Shifting Attention) will assess neurocognitive functions.

**Compensation:** Participants will be compensated \$50 for the baseline visit, \$50 for each imaging visit, \$40 for each completed weekly visit, and \$75 for completing each of the follow-up visits. They will be given a \$25 bonus if the baseline/first visit is attended as scheduled. Participants who previously consented to the optional neuropeptide Y will receive \$15 compensation for completing the second blood draw. Thus, participants may receive up to \$755 for completing all visits. Compensation is available in the form of cash, gift card, or check.

Telehealth participants will be offered compensation for travel to and from the three mandatory in-person visits (Baseline, Week 4, & Week 8).

**Neuroimaging Component:** Given the severe negative outcomes associated with co-occurring AUD/SUD and PTSD and lack of effective treatments, investigation of the neural circuitry and neurochemistry underlying AUD/SUD/PTSD and involved in positive therapeutic response could be important in guiding future treatment development studies. To that end, fMRI and H-MRS data will be acquired at baseline and end of treatment on a subset (n=40) of participants to examine (a) glutamate concentrations, (b) resting state connectivity, and (c) response to alcohol/drug, trauma, and neutral cues. Scans will be conducted at the MUSC Center for Biomedical Imaging.

The neuroimaging component will involve three visits, each lasting 60-90 minutes. During visit 1, we will develop the personalized imagery scripts for alcohol/drug, trauma, and neutral cues. During visit 2 (pre-treatment) and visit 3 (end of treatment), we will conduct the fMRI and H-MRS scanning procedures. Imagery scripts will be similar to those developed according to standardized procedures (Sinha & Li, 2007) and employed in our ongoing research.

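### As written, telehealth participants would probably have no pre-treatment EtG: the first sample falls at medication initiation, without the telehealth exception given to riboflavin

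*Combined protocol and SAP*

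**What the plan says.** The EtG entry under Alcohol/Substance Use Disorder and Craving describes a urine marker assayed in the study's laboratory on "samples collected at medication initiation, week 4, week 8 (end of treatment), and the follow ups". In Table 1 the EtG row is marked at week 0, week 4, week 8 and follow-up, and the baseline (week -1) cell is empty. Text and table agree.

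The Compensation paragraph offers telehealth participants payment for travel to "the three mandatory in-person visits (Baseline, Week 4, & Week 8)". Medication initiation is not in that list, and neither are the follow-up visits.

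The Riboflavin Test entry, under Vital Signs, Adverse Events and Medication Compliance, makes a provision for this group: "A urine assay will be collected at medication initiation (at baseline for telehealth participants), week 4 and week 8". The EtG entry contains nothing similar.

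In the analysis text for Hypothesis 1, EtG is named as an outcome beyond the primary ones: "Additional alcohol/substance use outcomes will be assessed: change in percent drinking days, percent heavy drinking days, EtG, and VAS craving levels". The same paragraph says that baseline substance use and craving will be covariates in the relevant models.

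**The concern.** If telehealth participants do not come in at medication initiation, the first EtG sample scheduled for them cannot be taken under the procedures described. Their earliest EtG would then be at week 4, after treatment has started. The value cannot be recovered later if the baseline urine was neither assayed nor kept.

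EtG has a specific job here. One primary outcome, total standard drinks, is self-reported through the TLFB. The breathalyzer and the telehealth saliva strip measure only current blood alcohol, and the listed urine drug panel does not include alcohol. The protocol justifies EtG because "EtG remains positive in urine for several days following cessation". It is therefore the only biological measure in the plan that looks back over several days of drinking. Without a pre-treatment value, EtG change cannot be calculated for telehealth participants, and a model that adjusts EtG for its own baseline would have no covariate value for them.

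**Working it through.** The plan states no figure on this point, so the check sets the schedules side by side and then sizes the gap under assumed telehealth shares.

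| | Baseline (wk -1) | Initiation (wk 0) | Week 4 | Week 8 | Follow-up (1 and 3 months) |
|---|---|---|---|---|---|
| EtG, text and Table 1 | no | yes | yes | yes | yes |
| Mandatory in-person visits for telehealth participants, Compensation | yes | not listed | yes | yes | not listed |
| Riboflavin urine, Table 1 | no | yes | yes | yes | no |
| Riboflavin urine for telehealth participants, Riboflavin Test text | yes | moved to baseline | yes | yes | no |
| Urine drug screen, Table 1 | yes | no | yes | yes | yes |

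**Step 1: overlap.** EtG times {week 0, week 4, week 8, follow-ups} and mandatory telehealth in-person visits {Baseline, week 4, week 8} share only {week 4, week 8}. Both come after treatment starts, so the number of pre-treatment EtG samples at a mandatory in-person visit is 0.

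**Step 2: is week-0 urine really unavailable?** The protocol does not say outright that initiation is remote for telehealth participants. Two things support the inference. Initiation is absent from the list of mandatory in-person visits. And the riboflavin clause would not be needed if urine could be had from these participants at week 0. The protocol describes no mailed or home urine collection. It does replace the breathalyzer with an on-camera saliva strip for telehealth visits, but gives no counterpart for EtG.

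**Step 3: what Table 1 adds.** The empty EtG baseline cell is not independent evidence. The riboflavin cell at baseline is also empty, although the text moves that sample for telehealth participants. The table does not show telehealth variations, so the point rests on the text.

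**Step 4: size.** Planned N is 90 (Participants). The telehealth share p is not given. Number affected = 90 × p:
- p = 10%: 90 × 0.10 = 9
- p = 30%: 90 × 0.30 = 27
- p = 50%: 90 × 0.50 = 45

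These counts illustrate a range and are not estimates.

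**Step 5: what can still be analysed.** Weeks 4 and 8 are in-person for everyone, so on-treatment EtG is obtainable in both visit modes. The TLFB covers the 60 days before study entry, so baseline drinking is available as a covariate for telehealth participants too. What is lost is the EtG change score and adjustment for baseline EtG.

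**The case against.** The strongest reply is that this is a wording omission on an additional outcome. The list of in-person visits sits in a sentence about travel payment. It says which visits are mandatory in person and does not forbid others, so some telehealth participants might attend at initiation. Baseline urine is collected anyway for the drug screen, and staff might use it for EtG. The analysis text plans adjustment for baseline substance use, not specifically for baseline EtG. The words introducing change in the outcome list may apply only to percent drinking days, in which case EtG at weeks 4 and 8 may be all that is intended.

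Much of this stands. It is why the conclusion is worded as probable and confined to change scores and baseline-EtG adjustment. It does not remove the point: nothing tells staff to run EtG on baseline urine, and for riboflavin the protocol put the same exception in writing.

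Three stronger readings are tempting, and the documents do not support them.

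- A reader might infer that the gap biases the treatment comparison, since it follows visit mode and is not random. Nothing links visit mode to treatment arm, and on-treatment EtG is obtainable in both modes.
- A reader might infer that ten telehealth participants (10/90 = 11.1%) would trigger the plan's imputation rule for more than 10% missing data. The Statistical Analyses paragraph does not say whether the percentage is per variable, per visit or overall. The same ten missing week-0 values are 10/270 = 3.7% of the three treatment-phase EtG samples and 10/450 = 2.2% of all five scheduled samples. It is also unclear whether a sample that could not be collected as scheduled counts as missing.
- A reader might infer that follow-up EtG must be restricted to in-person participants. The documents list no mandatory in-person follow-up visit for telehealth participants, but they do not exclude attendance. A restriction could discard valid samples.

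**Conclusion.** The point holds as a correctable gap in the collection schedule. Followed literally, the plan would probably leave telehealth participants without a pre-treatment EtG, so an EtG change score or an analysis adjusted for baseline EtG could not be computed for them. The primary outcomes (total standard drinks, OCDS, CAPS-5) are unaffected. The arms can still be compared on EtG at weeks 4 and 8 with TLFB baseline adjustment, and no bias between arms is shown.

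This rests on one inference, that week-0 urine is not available from telehealth participants, and on the absence of any described remote collection. The size depends on the unstated telehealth share: 9 to 45 of 90 over the assumed range of 10% to 50%.

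**What to change.** Add to the EtG entry the telehealth clause that the riboflavin entry already has, so that the first sample is taken at medication initiation, or at baseline for telehealth participants. Leave weeks 4 and 8 and the follow-ups as they are. Annotate the EtG row of Table 1 to match. For telehealth participants, run the first assay on urine collected at the in-person baseline visit. The documents give no volume or storage details for that urine, so the procedure should make sure that enough is kept for EtG.

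The cost is one clause and one table note. No visit is added, and the number of assays per participant is unchanged. The downside is that the first telehealth sample falls about one week earlier than for in-person participants and so reflects drinking over a different period. That is a small price compared with having no pre-treatment value.
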